3.1 General Design

Phase II Trial of Lenalidomide (Revlimid[®]) + Rituximab with and without Dexamethasone in recurrent small B cell non-Hodgkin lymphomas (NHL) resistant to Rituximab:

[^] Close monitoring for tumor lysis syndrome (TLS) should be initiated concurrent with the initiation of lenalidomide-dexamethasone in Part I (see Section 3.2). Subjects will receive tumor lysis prophylaxis if clinically indicated. All subjects should remain well hydrated during at least the first 7 days of Cycle 1. Close monitoring for TLS and the need for TLS prophylaxis should be repeated during at least the first 7 days of Part II treatment. Additional TLS monitoring and prophylaxis may be employed at any time at the investigator's discretion. Tumor flare occurring during the first 1-2 weeks of Cycles 1, 2 and 3 should be recorded as AEs and not as progressive disease (PD). Tumor flare should be treated symptomatically with non-steroidal anti-inflammatory agents (NSAIDs) and other measures as needed

* Follow-up staging 3 months after first dose of Rituximab (i.e after 5 months) then after months 12, 18 and 24 (as counted from enrollment of trial), then yearly until disease progression, development of unacceptable toxicity, or voluntary withdrawal, whichever occurs first.

† In patients with absolute lymphocyte count >20,000/ μ l, prior to rituximab infusion, close monitoring for tumor lysis syndrome should be initiated and those patients should receive appropriate supportive care (e.g., allopurinol, intravenous hydration, additional laboratory test monitoring, etc.). A modified dosing scheme is suggested for those patients with absolute lymphocyte count >20,000/ μ l (see 6.2)

At time of progression or relapse, a biopsy is recommended. If a biopsy is performed, and the patient consented to allow their tissue to be kept for future unknown use, the pathology specimen will be asservated at the U Penn Tissue Core facility.

Subjects with CR, PR, SD or PD with an estimated life expectancy of >3 months will continue to Part II of the trial

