In Part I of the study, subjects in both cohorts will receive lenalidomide 10 mg PO once daily on Days 1-28 every 28 days for two 28-day cycles. Subjects in Cohort 1 will also receive dexamethasone 8 mg PO once weekly (dosing on Days 3, 10, 17 and 24 is suggested, but not required) for two 28-day cycles. Serum and plasma samples for ancillary studies will be collected for all subjects upon entry into the trial, after 2 cycles of study therapy, and at the investigator's discretion in subjects with extended remissions. Subjects will be restaged after the first 2 cycles (Part I) prior to Part II and will continue with Part II (with rituximab) unless progression of disease is documented with life expectancy estimated to be <3 months during Part I.

In Part II, all subjects will receive lenalidomide once daily Days 1-28 over 28 days as well as Rituximab 375mg/m² IV once weekly during cycle 3. Subjects enrolled in Cohort 1 will also receive dexamethasone PO once weekly during each 28 day treatment cycle. The doses of lenalidomide and dexamethasone (for subjects in Cohort 1) during Part II will be determined by dose modification guidelines in Section 6. All subjects will be restaged 3 months after first rituximab infusion (prior to cycle 6). Again, serum and plasma samples for ancillary studies will be collected at this point. Following Part II, subjects in Cohort 1 will continue on lenalidomide once daily on Days 1-28 every 28 days and dexamethasone once weekly until disease progression, development of unacceptable toxicity, or voluntary withdrawal, whichever occurs first.

Subjects in Cohort 2 will continue on lenalidomide once daily on days 1-28 of each 28 day cycle. Restaging for all subjects will be performed on months 12, 18 and 24 (as counted from enrollment of trial) and then yearly until disease progression, development of unacceptable toxicity, or voluntary withdrawal, whichever occurs first. These restaging assessments may be performed +/- 2 months from these timepoints, or at the clinical discretion of the treating physician.

Subjects are required to receive prophylactic anti-coagulation with aspirin, Coumadin or low molecular weight heparin due to the increased risk of thrombosis reported with lenalidomide therapy. Coumadin should only be used with caution and close monitoring of INR. Prophylactic anti-coagulation should be held for platelet counts $< 50,000/\text{mm}^3$ and restarted when platelet counts are $\geq 50,000/\text{mm}^3$.

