3.3 Table of Events

Tests & Observations (see footnote M)	Prior to study	Prior to starting Cycles 1-6	Restaging after Part I	Restaging after Part II and subsequent follow- up*
History	X			
Physical Examination	X	X	X	X
Height	X			
Weight, BSA**	X		X	
Performance Status	X	X	X	X
Tumor measurements	X	A	X	X
Drug toxicity Assessment		X	X	X,N
Register into Revlimid REMS® program	X,O			
EKG	X			
Laboratory Studies (see footnote M)				
CBC, Differential, Platelets	X	X,H	X	X
Serum Creatinine, BUN	X	X,	X	X
Serum Electrolytes	X	X,	X	X
Total Protein, Albumin	X	X	X	
AST,ALT, Alk. Phos., Bilirubin	X	X	X	X
ESR, CRP, Fibrinogen	X^	X, ^	X^	X,C^
Uric acid/Phosphate/LDH/Ca ⁺⁺	X	X,J	X	X,C
Serum or urine b-HCG***	X, B	B	X	B
Serum IgG, IgA, IgM	X^	X,C^	X^	C^
FCR Polymorphism Sample (see 3.5)	X^			
Blood and Plasma Sample (see 3.5)	X		X	D
HACA				E^
HBsAg, HepCAb, HBcAb	F			F
TSH (repeat only if clinically indicated)	X			
Staging (see footnote M)				
CT / MRI (chest/abd/pelvis) / PET-CT	X		X	X
CT Scan/MRI (neck)	G		G	G
Bone Marrow Asp& BX (unilateral)	P		K	K
Histologic Review	X		L	L

* Follow-up staging on months 12, 18 and 24 as counted from enrollment, then yearly until disease progression, development of unacceptable toxicity, or voluntary withdrawal, whichever occurs first. Physical exams and study labs should be done monthly for the first 6 months, every two months for cycles 7-13 and every three months thereafter (+/- 2 weeks). After the first 6 months of weekly labs, subjects will continue to have a CBC monthly while on-study.

** Although doses are recalculated prior to each treatment, the actual dose of rituximab to be given need not change unless the calculated dose changes by $\geq 10\%$. NOTE THAT LENALIDOMIDE DOSES ARE NOT BASED ON WEIGHT OR BSA.

*** Pregnancy tests for females of childbearing potential. A female of childbearing potential (FCBP) is a sexually mature female who: 1) has not undergone a hysterectomy or bilateral oophorectomy; or 2) has not been naturally postmenopausal for at least 24 consecutive months (i.e., has had menses at any time in the preceding 24 consecutive months).

[^] Subjects enrolled into Cohort 1 only. Not applicable for subjects enrolled into Cohort 2.

A If accessible to physical examination, please record measurements

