7.9 Time to progression (TTP)

TTP is defined as the time from the first day of protocol therapy to the first event defining progression of disease or last subject contact. TTP is defined for all subjects receiving protocol therapy, following an intent-to-treat analysis plan. TTP from rituximab is defined for patients receiving rituximab (Part II) from the first day of rituximab therapy to the first event defining treatment failure.

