Time to progression. We will compute a 95% confidence interval for the ratio of median TTP under revlimid+rituximab to the median TTP under rituximab alone, using the nonparametric method of Jung and Su (1995). If the interval excludes 1, we will declare the difference to be statistically significant.

To evaluate the power of this design, we assumed that TTP in the baseline (rituximab only) period would be statistically independent of TTP in the follow-up (combination treatment) period. This will lead to a conservative estimate of the power, as positive correlation of failure-time endpoints generally increases power for paired comparisons (e.g., see Mick et al. 2000). Assuming that median TTP in the baseline period is 3 months, we calculated the power to detect significance in a test of the null hypothesis that median TTP is the same in both periods. If the median TTP in the follow-up period is doubled, to 6 months, then the power is 83%; if the median TTP is tripled, to 12 months, then the power is essentially 100%. Thus power is satisfactory if there is a substantial increase in the median TTP.

Design and analysis of correlative studies. In correlative studies, we will compare mean changes in immunologic phenotype parameters (fraction Th2⁺ cells, NK cells and Treg cells) between the subjects who experience a remission (expected to be up to 80%, or 36 of 45 subjects) and those who do not (as few as 20%, or 9 of 45 subjects). As we do not yet know the likely values of these immunologic parameters, we estimate the power in terms of the difference in means as a fraction of the common standard deviation (SD). The basic analysis is a t test comparing mean change in the two groups. Calculations show that if the standardized difference is equal to 1 SD, then the power is 75%, whereas if the standard difference is 1.25 SDs, then the power is 91%. Thus the power of this correlative analysis is reasonable as long as there is a reasonably large difference in mean change between the remission and non-remission groups.

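### Time to progression has no dating or interval-censoring rule under a sparse staging calendar, so on-study TTP can only err late and its ratio to prior TTP can be overstated

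*Combined protocol and SAP*

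**What the plan says.** Section 3.1 sets the staging calendar. "Subjects will be restaged after the first 2 cycles (Part I) prior to Part II", and then "All subjects will be restaged 3 months after first rituximab infusion (prior to cycle 6"). After that, "Restaging for all subjects will be performed on months 12, 18 and 24 (as counted from enrollment of trial"). A footnote in the same section gives the sequence as "Follow-up staging 3 months after first dose of Rituximab (i.e after 5 months) then after months 12, 18 and 24", followed by yearly staging. The text adds a window: "These restaging assessments may be performed +/- 2 months from these timepoints, or at the clinical discretion of the treating physician".

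Between scans, the Table of Events (3.3) has clinic visits: "Physical exams and study labs should be done monthly for the first 6 months, every two months for cycles 7-13". Section 7.6 lets a new lesion above 1 cm on physical examination count as progression.

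Section 7.9 runs TTP from the first day of therapy "to the first event defining progression of disease or last subject contact". Section 8 forms a 95% interval for the ratio of on-study to prior median TTP by the Jung and Su method, and declares significance if that interval excludes 1. The prior median is taken as 3 months. On power it says "If the median TTP in the follow-up period is doubled, to 6 months, then the power is 83" (per cent).

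The plan has no rule for dating progression that occurred between two assessments, no interval-censored analysis, and no account of how or how often progression on the prior rituximab regimen was assessed.

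**The concern.** A ratio of medians treats each TTP as an exact time. On study, progression is known only to lie between the last assessment without it and the first with it. Dating it at the later one, the ordinary reading of 7.9, makes every on-study TTP too long or correct, never too short. The planned 6-month median falls between the month-5 and month-12 stagings, so the reported median is set largely by the calendar.

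The prior TTP in the denominator was dated in some other way. If its delay was smaller, the two delays do not cancel and the ratio leans towards benefit. This comparison is the first secondary objective (2.2.1) and has its own significance rule, so both the estimate and the claim are exposed.

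**Working it through.** **Inputs.** N = 45, prior median 3 months, on-study median 6 months, independent periods (Section 8). Stagings at 56 days (about 1.84 months), month 5, months 12, 18 and 24, then yearly (3.1). Visits at months 6, 8 and 10 between the month-5 and month-12 scans (3.3). Assumption: exponential TTP, since the plan names no distribution.

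**The plan's own figure.** A two-sided paired Wilcoxon signed-rank test on exact TTPs gives 83.5% power for 3 versus 6 months, matching the stated 83%. A percentile-bootstrap interval for the ratio of medians gives about 60%, and an approximation to Jung and Su about 48%. So the stated power fits a different test from the one planned. This is a side point. The bootstrap stands in for Jung and Su below.

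**Step 1: median under scheduled scans only.** P(T ≤ t) = 1 − 2^(−t/6).
- Month 5: 1 − 2^(−5/6) = 0.439.
- Month 12: 1 − 2^(−2) = 0.750.

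The 50% point is first crossed at the month-12 scan, so the median reads 12, or 10 to 14 over the window. With Weibull shapes 1 to 2 the two fractions are 38–44% and 75–94%, so the reading does not depend on the exponential form. In simulated 45-patient trials the observed median was 12 in about 80% and 5 in about 20%.

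**Step 2: allow detection between scans.** Let f be the share of progressions after month 5 found at interim visits. The median reads t or less when f ≥ (0.5 − 0.439) / (S(5) − S(t)), with S(5) = 0.561.
- t = 10: 0.0612 / (0.5612 − 0.3150) = 0.25.
- t = 8: 0.0612 / (0.5612 − 0.3969) = 0.37.
- t = 6: 0.0612 / (0.5612 − 0.5000) = 1.00.

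So it reads about 10 at f = 25%, 8 at f = 50%, and 6 only if every such progression is found at a visit.

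**Step 3: the ratio.** True value 6/3 = 2.0. With scheduled scans only and exact prior dates it is 12/3 = 4.0 (10/3 = 3.3 to 14/3 = 4.7 over the window). If prior progression was read on three-monthly scans (an assumption), the prior median reads 3 to 6 and the ratio 2 to 4. With exact prior dates, the bootstrap interval excludes 1 in about 91% of trials, against 60% with exact dates in both periods.

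**Step 4: no benefit, both medians 3 months.** P(T ≤ 1.84) = 1 − 2^(−1.84/3) = 0.346 and P(T ≤ 5) = 1 − 2^(−5/3) = 0.685, so the on-study median reads 5 and the ratio 5/3 = 1.67. Share of simulated trials whose nominal 95% interval excludes 1, with no between-scan detection:

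| On-study staging | Prior dating | Excludes 1 |
|---|---|---|
| exact | exact | about 4% |
| as planned | exact | about 43% |
| planned, plus scans at months 7, 8 and 10 | exact | about 42% |
| near-monthly to month 5, then as planned | exact | about 6% |
| as planned | monthly or two-monthly | about 15% |
| as planned | three-monthly | about 3% |

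Repeat runs move these by a point or two. With exact prior dates, 25% or 50% between-scan detection lowers the 43% to about 28% or 20%.

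**The case against.** The strongest reply is that scheduled scans are not the only route to a progression date. Restaging may follow physician discretion, examinations continue every one to two months through cycle 13, and a palpable new lesion counts as progression. All of this stands and shrinks the bias, as Step 2 shows. It does not remove it: no interim scan is required, and 3.4 treats clinical lesions as measurable only when superficial.

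Three stronger readings are tempting and are not supported.
- A reader might infer that the ratio is inflated as a matter of fact. That depends on how prior progression was dated. With three-monthly prior dating the null rejection rate is nominal in this calculation.
- A reader might blame the 7-month gap for the false-positive rate. Filling the gap leaves it at about 42%; shortening the month 1.8-to-5 interval brings it to about 6%. The later gap distorts the size of a real effect instead.
- A reader might say the median cannot tell 6 months from 12. Under scheduled scans only, a true 6 reads 5 in about 20% of trials, while a true 12 reads 12 in about half and 18 or later in the rest. Discrimination is poor but not absent.

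Dating at detection is also an inference from 7.9. The documented fact is that no rule is given.

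**Conclusion.** The point holds in conditional form. The plan feeds coarsely observed progression times into an exact-time method with no dating rule, and the on-study error can go only one way. A true 6-month median reads 12 months with scheduled detection alone, and about 8 to 10 with 25% to 50% clinical detection. The ratio can read up to about 4 instead of 2.

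Under no benefit, the significance rule fails in about 3% to 43% of trials depending on prior dating. The top of that range needs exactly dated prior progression and no between-scan detection, so it is an extreme and not an expected value. These figures rest on exponential, independent TTPs and a percentile bootstrap in place of Jung and Su.

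TTP is secondary. The response assessments after Part I and at three months post-rituximab are unaffected.

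**What to change.** In 7.9 and Section 8:
- Record for each patient the last assessment without progression and the first with it, and state whether a negative physical examination counts as an assessment.
- Report an interval-censored on-study TTP median beside the Jung and Su ratio, as a range when it falls between scans. State in advance which point of that range enters the ratio.
- Record how and when progression on the prior regimen was ascertained, and interval-censor that period where last-negative dates exist.
- Do not claim significance from the ratio unless it also holds in this sensitivity analysis.

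No extra scans and no change to patient management are needed. The cost is SAP wording, some record abstraction, and a wider and less favourable interval. Last-negative dates for the prior regimen may be missing for some patients, which is why Jung and Su stays as planned and is not replaced.

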3.2 Required Data

Guidelines for pre-study testing

To be completed within 60 days before registration:

- Radiological imaging (e.g., CT or MRI) which is utilized for tumor measurement. If a fusion PET-CT has been obtained and is deemed satisfactory for anatomic evaluation of lesions, a separate diagnostic contrasted CT study will not be required.
- Review of diagnostic pathology material to confirm the diagnosis
- Paraffin blocks and/or frozen material from the initial biopsy or biopsy at relapse will be requested in all cases, but are not required for protocol eligibility.

To be completed within 28 days before registration, or on date of registration

- All blood studies
- History and physical exam

3.3 Table of Events

Tests & Observations (see footnote M)	Prior to study	Prior to starting Cycles 1-6	Restaging after Part I	Restaging after Part II and subsequent follow- up*
History	X			
Physical Examination	X	X	X	X
Height	X			
Weight, BSA**	X		X	
Performance Status	X	X	X	X
Tumor measurements	X	A	X	X
Drug toxicity Assessment		X	X	X,N
Register into Revlimid REMS® program	X,O			
EKG	X			
Laboratory Studies (see footnote M)				
CBC, Differential, Platelets	X	X,H	X	X
Serum Creatinine, BUN	X	X,	X	X
Serum Electrolytes	X	X,	X	X
Total Protein, Albumin	X	X	X	
AST,ALT, Alk. Phos., Bilirubin	X	X	X	X
ESR, CRP, Fibrinogen	X^	X, ^	X^	X,C^
Uric acid/Phosphate/LDH/Ca ⁺⁺	X	X,J	X	X,C
Serum or urine b-HCG***	X, B	B	X	B
Serum IgG, IgA, IgM	X^	X,C^	X^	C^
FCR Polymorphism Sample (see 3.5)	X^			
Blood and Plasma Sample (see 3.5)	X		X	D
HACA				E^
HBsAg, HepCAb, HBcAb	F			F
TSH (repeat only if clinically indicated)	X			
Staging (see footnote M)				
CT / MRI (chest/abd/pelvis) / PET-CT	X		X	X
CT Scan/MRI (neck)	G		G	G
Bone Marrow Asp& BX (unilateral)	P		K	K
Histologic Review	X		L	L

* Follow-up staging on months 12, 18 and 24 as counted from enrollment, then yearly until disease progression, development of unacceptable toxicity, or voluntary withdrawal, whichever occurs first. Physical exams and study labs should be done monthly for the first 6 months, every two months for cycles 7-13 and every three months thereafter (+/- 2 weeks). After the first 6 months of weekly labs, subjects will continue to have a CBC monthly while on-study.

** Although doses are recalculated prior to each treatment, the actual dose of rituximab to be given need not change unless the calculated dose changes by $\geq 10\%$. NOTE THAT LENALIDOMIDE DOSES ARE NOT BASED ON WEIGHT OR BSA.

*** Pregnancy tests for females of childbearing potential. A female of childbearing potential (FCBP) is a sexually mature female who: 1) has not undergone a hysterectomy or bilateral oophorectomy; or 2) has not been naturally postmenopausal for at least 24 consecutive months (i.e., has had menses at any time in the preceding 24 consecutive months).

[^] Subjects enrolled into Cohort 1 only. Not applicable for subjects enrolled into Cohort 2.

A If accessible to physical examination, please record measurements

B Pregnancy tests must occur within 10 – 14 days and again within 24 hours prior to prescribing lenalidomide (prescriptions must be filled within 7 days). FCBP with regular or no menstruation must have a pregnancy test weekly for the first 28 days and then every 28 days while on therapy (including breaks in therapy); at discontinuation of lenalidomide and at Day 28 post the last dose of lenalidomide. Females with irregular menstruation must have a pregnancy test weekly for the first 28 days and then every 14 days while on therapy (including breaks in therapy), at discontinuation of lenalidomide and at Day 14 and Day 28 post the last dose of lenalidomide (see Appendix A: Risks of Fetal Exposure, Pregnancy Testing Guidelines and Acceptable Birth Control Methods).

C Perform for the first 6 cycles

D Obtained prior to beginning Cycle 6 and at the investigator's discretion in subjects with durable remissions.

E Perform upon completion of rituximab therapy (before initiation of Cycle 4) and at the End of Cycle 10

F Patients with known hepatitis B or C are not eligible for this study. Negative results are required for participation. This will be based on the subject's medical history. Note: Baseline Hepatitis B/C testing is not required.

G Perform if nodes are palpable.

- H Weekly throughout cycles 1-6, monthly thereafter.
- J During Cycles 1 on Day 3, 4, or 5 and on Day 8. During the cycle of rituximab therapy (cycle 3) on Days 3, 4, or 5, and on Days 8 to monitor for tumor lysis syndrome. Additional assessments may be done at any time.
- K If initially positive, repeat only in patients who are demonstrated to be in CR/Cru by all other criteria.
- L At time of progression or relapse, a biopsy is recommended to be performed. If a biopsy is performed, patients may separately consent to allow their tissue to be kept for future unknown research.
- M If Physical examination, vital signs, weight and ECOG performance status were done within 7 days of Day 1, they do not need to be repeated at Study Day 1. An unscheduled visit can occur at any time during the study. Source must be maintained for these unscheduled visits. The date for the visit and any data generated must be recorded on the appropriate CRF. Source documents for these unscheduled visits must also be maintained.
- N An additional safety assessment will be done 30 days (+/- 7 days) following the last dose of study drug.
- O Lenalidomide must be prescribed through and in compliance with the Revlimid REMS® program of Celgene Corporation. Prescriptions must be filled within 7 days. Consideration should be given to prescribing lenalidomide 5 to 7 days in advance of Day 1 of each cycle to allow time for required patient and prescriber surveys, and drug shipment to patient. Any unused Revlimid® (lenalidomide) should be returned to the patient for disposition in accordance with the Revlimid REMS® program.
- P If patient has a history of bone marrow involvement at baseline.

